5. STUDY DRUG PRODUCT

5.1. Randomization, Blinding and Treatment Codes

5.1.1. Procedure for Subject Randomization

Subjects will be randomized to one of the two Treatment Groups on a 2:1 basis (NB01 or vehicle-control) using a central randomization scheme. Randomization will be stratified by sex (male/female) and age (18-25 years old/26-40 years old).

Subjects will be randomized on Day 1 after the subject has arrived at the site and eligibility has been confirmed. To randomize a subject the PI or designee will call the contract research organization (CRO) and provide the required subject information. The CRO will have a designated unblinded staff member available to assign a study drug kit number to the subject, which contains the treatment specified by the randomization schedule. A subject randomization form documenting study drug kit number assignment will be provided to the site by the CRO.

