Non-systemic (local) AEs Grade 3 or higher for which there is no clear alternative explanation of the cause of the AE will also be considered DLTs. Any subject who experiences a DLT, as described above, must discontinue treatment and be scheduled for a final visit. Any DLTs that are Grade 2 or greater systemic AEs must be reported by the PI immediately. If three or more subjects experience DLTs in the study, enrollment in the study will be halted, and a safety review will occur using an independent medical reviewer who will have access to the subject's treatment allocation. This review shall be completed promptly within 10 business days. Subjects who are active in the study will be instructed to withhold study drug applications during the safety review period. If all of the subjects experiencing DLTs (i.e. three or more) are found to be subjects receiving the active NB01 study drug, the independent medical reviewer will provide a written recommendation to the Sponsor to continue the study, discontinue the study or modify the study protocol. The Sponsor is responsible for promptly reviewing the independent medical reviewer's recommendations, accepting or rejecting these recommendations, and determining whether amendments to the protocol or changes in study conduct will be required. The Sponsor will provide the final written decision regarding the study status. In the event this is not the case, the independent medical reviewer will notify the Sponsor and Medical Monitor of how many subject's DLTs were in subjects receiving vehicle (e.g. Y subjects). In the event Y new subjects experience DLTs, the independent medical reviewer review process outlined above will be repeated. This process will be repeated throughout the entire study until the study is complete or

the stopping rule has been met. In the event that a total of three (3) or more subjects experience DLTs related to NB01 study drug, the study will be discontinued.

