If an SAE occurs during the study and is determined by the Sponsor to be at least possibly related to the study drug, enrollment of new subjects and dosing of active subjects will be halted. A safety review will occur using an independent medical reviewer who will have access to the subject's treatment allocation. This review shall be completed promptly within 5 business days. The independent medical reviewer will provide a written recommendation to the Sponsor to continue the study, discontinue the study or modify the study protocol. The Sponsor is responsible for promptly reviewing the independent medical reviewer's recommendations, accepting or rejecting these recommendations, and determining whether amendments to the protocol or changes in study conduct will be required. The Sponsor will provide the final written decision regarding the study status. A summary of the event should also be reported to FDA as part of an IND Safety Report in accordance with Section 7.2.2. FDA should also be notified within 48 hours of the final decision and provided an IND Safety Follow-up Report as necessary (if new information was collected since the initial Safety Report).

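### The repeat trigger for DLT reviews matches the three-subject limit only if the first review covers exactly three subjects; with n above three, the next review can come up to n − 3 DLT subjects late

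*Protocol*

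**What the plan says.** Protocol 7.2.1 sets the DLT rule in four steps.

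- **First review.** "If three or more subjects experience DLTs in the study, enrollment in the study will be halted". An independent medical reviewer with access to treatment allocation then has 10 business days. The wording sets a floor of three, not a cap, and the branch for DLTs that are all on NB01 again allows for more than three.
- **What is reported.** If not all cases are on NB01, the reviewer tells the Sponsor and Medical Monitor how many "DLTs were in subjects receiving vehicle (e.g. Y subjects").
- **Repeat review.** "In the event Y new subjects experience DLTs, the independent medical reviewer review process outlined above will be repeated". This continues until the study is complete or the stopping rule is met.
- **Stopping limit.** "In the event that a total of three (3) or more subjects experience DLTs related to NB01 study drug, the study will be discontinued".

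Two further sentences in the same section matter. On reporting speed: "Any DLTs that are Grade 2 or greater systemic AEs must be reported by the PI immediately". No equivalent duty is stated for local Grade 3 DLTs. On dosing: "Subjects who are active in the study will be instructed to withhold study drug applications during the safety review period". SAP 8.12.2 says only that DLTs will be summarized and adds no rule.

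**The concern.** The repeat trigger should bring the reviewer back no later than the moment at which the limit could be met. Y does this when three subjects have been reviewed, because the vehicle count then equals the number of further NB01 cases needed to reach three. It does not when four or more have been reviewed, which the text permits.

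A first review of four is possible if DLTs occur close together, if a local Grade 3 DLT surfaces late, or if a DLT found during the 10 business days is added to the review in progress. In that case NB01 could reach three subjects with DLTs while others keep dosing, because the review that would show it is not yet due. The trial is blinded, and 7.2.1 assigns nobody to count NB01 cases between reviews. Protocol 5.1.1 does mention an unblinded person ("The CRO will have a designated unblinded staff member available to assign a study drug kit number to the subject"), but gives that person no part in the DLT count.

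Safety is the primary objective, so the rule should work in every case that its own wording allows.

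**Working it through.** **Inputs.** Review floor of three, definition of Y, repeat trigger and limit of three: Protocol 7.2.1. Thirty-six subjects: Protocol 3.3. Allocation 2:1: Protocol 5.1.1. The documents give no DLT rate.

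**Counting.** Let a first review cover n DLT subjects, a of them on NB01, so Y = n − a. Here a DLT related to NB01 is taken to mean a DLT in a subject on NB01.

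- Fewest further DLTs that can bring NB01 to three: 3 − a.
- Protocol trigger: Y = n − a.
- Gap: (n − a) − (3 − a) = n − 3.

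The trigger matters only if a ≤ 2; otherwise the limit is already met at the first review.

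| n | Y | NB01 (a) | Needed (3 − a) | Trigger (Y) | Gap |
|---|---|---|---|---|---|
| 3 | 1, 2, 3 | 2, 1, 0 | 1, 2, 3 | 1, 2, 3 | 0 |
| 4 | 2, 3, 4 | 2, 1, 0 | 1, 2, 3 | 2, 3, 4 | 1 |
| 5 | 3, 4, 5 | 2, 1, 0 | 1, 2, 3 | 3, 4, 5 | 2 |

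The protocol's rule is reproduced exactly at n = 3. The gap is a worst case: it is realised in full if the new DLTs are on NB01, and NB01 then stands at a + Y = n when the review falls due. If some new DLTs are on vehicle, the delay is shorter or nil.

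**Repeat reviews.** After a first review of three there is no delay if Y and new cases are both counted since the last review, or both from the first. There is delay only if Y accumulates while the count of new cases restarts. In all 16,278 orders of 14 DLTs with at least three on NB01 (2^14 − 1 − 14 − 91), the two consistent readings give 0 late orders and the mixed one 7,688. With a first review of four, either consistent reading gives 6,948. These are counts of orders, not probabilities.

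**Illustration for n = 4.** Assumptions: 24 on NB01 and 12 on vehicle, DLTs continue to occur, and per-subject risk on NB01 is w times that on vehicle. With a NB01 and v vehicle DLTs so far, the next is on NB01 with probability w(24 − a) / [w(24 − a) + 12 − v].

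For w = 1:

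- Limit not yet met: P(2 NB01, 2 vehicle) = 276 × 66 / 58,905 = 0.309; P(1, 3) = 24 × 220 / 58,905 = 0.090; P(0, 4) = 495 / 58,905 = 0.008. Sum 0.407.
- Third NB01 DLT before the trigger: 22/32 = 0.688; (23/32)(22/31) = 0.510; (24/32)(23/31)(22/30) = 0.408. Weighted 0.643.
- Over all first reviews of four: 0.407 × 0.643 = 0.262.

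| NB01 risk relative to vehicle | Limit not met at review of four | Given that, third NB01 DLT precedes trigger | Given that, four or more NB01 DLTs at trigger | Over all reviews of four, third precedes trigger |
|---|---|---|---|---|
| 1× | 41% | 64% | 44% | 26% |
| 2× | 18% | 80% | 65% | 14% |
| 4× | 6% | 89% | 80% | 6% |

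The last column falls as NB01 risk rises, because the limit is then usually met at the first review itself.

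**How many DLTs this needs.** Any delay needs at least five DLT subjects. At assumed per-subject risks of 2%, 5% and 10%, the binomial probability of five or more among 36 is 0.07%, 3.2% and 29%. These are ceilings: they ignore the halts, and they do not yet require a first review above three with at most two on NB01.

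**The case against.** The strongest reply is that the ordinary path contains no error. Review starts at the third DLT, drug is withheld, and at n = 3 the trigger is exact. A fourth case has to be folded into the first review to create a gap. If it is counted as new instead (two NB01 and one vehicle, so Y = 1), re-review is immediate. This stands and narrows the point, but the text does not say which count applies, and it expressly allows more than three.

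Second, the limit is worded as relatedness, not allocation. When all DLTs are on NB01 the reviewer may still recommend continuing, which suggests that the two are judged separately. This also stands: if relatedness is judged more narrowly, the limit is reached later and the delay is smaller.

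Third, other safeguards exist. Each DLT subject stops treatment. A serious event has its own route ("If an SAE occurs during the study and is determined by the Sponsor to be at least possibly related to the study drug"), with a halt and an unblinded review. The stopping sentence is not tied to a scheduled review. The gap therefore concerns mainly non-serious DLTs; but between reviews a crossing would normally go unseen under the blind.

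A reader might infer that the trigger is always late, or that 64% to 89% is the chance of overrunning the limit in this trial. The documents support neither. The delay is zero at n = 3 with consistent counting, and those percentages are conditional on a first review of four that has not yet met the limit. The open counting basis at repeat reviews is a wording point, since the natural consistent readings are exact after a first review of three.

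**Conclusion.** The point holds in a limited form. When a first review covers n > 3 subjects and at most two are on NB01, the repeat trigger exceeds the number of DLTs that could complete three on NB01 by n − 3. The next review can then fall up to that many DLT subjects late: one at n = 4, two at n = 5. This rests on reading relatedness as a DLT in a subject on NB01, and the full delay needs the new DLTs to be on NB01. The percentages for n = 4 rest in addition on the assumed 24:12 split and relative risks; under narrower relatedness they are upper values.

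How often a first review would exceed three cannot be derived from the documents. Because Protocol 3.3 reports the 36 subjects as already randomized, the point bears on continued dosing more than on enrollment. It is a low-priority correction to a safety rule and does not show that the limit itself is wrong.

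**What to change.** In Protocol 7.2.1, replace the trigger of Y new subjects by three minus the number of NB01 subjects with DLTs to date, with new cases counted from the latest review. At n = 3 this is the current rule. At n = 4 it gives 1, 2, 3 for Y = 2, 3, 4, in place of 2, 3, 4. It has no gap for any n or at repeat reviews (0 late orders in the enumeration for first reviews of 3, 4 and 5), removes the question of how Y accumulates, and leaves the limit of three as it is. Alternatively, the independent reviewer could check the allocation of every DLT subject after the first review.

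The cost is a protocol amendment, which needs IRB approval before use (Protocol 9.2.1), and some earlier allocation look-ups. The trigger discloses no extra count, since n and Y already give the NB01 number. It does lead to slightly more reviews of a single new case, whose arm the reported count would reveal; the current rule already has this when Y = 1. If dosing has ended, the change has no use in this study.

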7.2.2. Serious Adverse Events

An event that is serious must be recorded on the CRF/eCRF and requires expeditious handling to comply with regulatory requirements.

An AE or suspected adverse reaction is considered "serious" if, in the opinion of either the PI or Sponsor, it results in any of the following outcomes:

- Death; the event must be the cause of death for the SAE to meet this serious criterion.
- Life-threatening event; an event in which the subject was at risk of death at the time of the event and not an event that hypothetically might have caused death if it had been more severe.
- Requires inpatient hospitalization or prolongation of existing hospitalization (for ≥ 24 hours).
- Persistent or significant incapacity or substantial disruption of the ability to conduct normal life functions.
- Congenital anomaly/birth defect.
- Important medical events; a medical event(s) that may not result in death, be life-threatening, or require hospitalization but, based upon appropriate medical judgment, may jeopardize the subject and may require medical or surgical intervention to prevent one of the outcomes listed in the definition above. Examples of such medical events include allergic bronchospasm requiring intensive treatment in an emergency room or at home, blood dyscrasias or convulsions that do not result in inpatient hospitalization, or the development of drug dependency or drug abuse.

Events NOT considered to be SAEs are:

- Hospitalizations for the treatment, which was elective or pre-planned, of a pre-existing condition that did not worsen; and

- Treatment on an emergency, outpatient basis, for an event not fulfilling any of the definitions of “serious” given above and not resulting in hospital admission.

AEs classified as “serious” by either the PI or the Sponsor require expeditious handling and reporting to the Sponsor or designee to comply with regulatory requirements. **All SAEs, whether related or unrelated to study drug, must be immediately reported by telephone to the Medical Monitor listed on the first page of the protocol. In the event that he/she is unavailable, contact the back-up Medical Monitor listed in the study reference manual.**

Written notification of all SAEs should be sent to the Trial Manager by email or confirmed facsimile transmission. These include those SAEs listed in the protocol or IB and must include an assessment of whether there is a reasonable possibility that the study drug caused the event.

Any suspected adverse reactions that are serious and unexpected represent especially important safety information that must be reported more rapidly to Health Authorities; therefore, it is important that the PI submit any information requested by the Sponsor or designee as soon as it becomes available.

If only limited information is initially available, follow-up reports are required. Should the PI become aware of an SAE (regardless of its relationship to study drug) that occurs within 30 days after stopping the study drug, the SAE must be reported in accordance with procedures specified in this protocol. In the event of death, if an autopsy is performed, a copy of the report should be sent to the Sponsor or designee, if available.

As required, the Sponsor or designee will notify participating PIs of all suspected adverse reactions that are serious and unexpected. This notification will be in the form of an IND safety report of potential serious risks as soon as possible but no later than 15 calendar days after the Sponsor determines that the information is “reportable” according to the criteria listed in 21 CFR Section 312.32. These are:

- i) Serious and unexpected suspected adverse reactions;
- ii) Findings from other studies including epidemiological studies, pooled analyses, or other clinical studies that suggest a significant risk in humans exposed to the study drugs;
- iii) Findings from animal or in vitro tests that suggest a significant risk to humans exposed to the study drugs, or reports of significant organ toxicity at or near the expected human exposure; and
- iv) Clinically important increases in the rate of occurrence of serious suspected adverse reactions.

Upon receiving such notices, the PI must review and retain the notice with the IB and promptly submit a copy of this information to the responsible IRB according to local regulations. The PI and IRB will determine if the informed consent requires revision. The PI should also comply with the IRB procedures for reporting any other safety information. Where required, submission of safety updates by the PI to Health Authorities should be handled according to local regulations.

The Sponsor or designee may be required to report certain SAEs to regulatory authorities (e.g., United States FDA) within seven calendar days of being notified about the event; therefore, it is important that PIs submit any information requested by the Sponsor or designee as soon as it becomes available.

7.2.3. Clinical Laboratory Abnormalities and Other Abnormal Assessments as Adverse Events or Serious Adverse Events

The PI will evaluate clinical laboratory results, physical exam findings and vital signs to determine if any findings are clinically significant. Any clinically significant results that represent and new or worsening change from Baseline should be recorded as an AE.

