6.2.4. Follow-up Assessment – Visit 6 (Week 16/End of Study/Day 106)

The following will be performed and documented during a telephone follow-up call with the subject:

- Assess AEs and LSRs. If the subject reports any worsening ongoing AEs or material new AEs, especially those that may potentially be related to the study drug, the subject will be scheduled for an office visit if, in the opinion of the PI, a clinical evaluation is warranted (e.g., a significant safety concern).
- Counsel the subject regarding the need for post study follow up with their primary care physician for any ongoing medical needs if indicated.
- Review concomitant medications, topical facial products and procedures/therapies.

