7.2. Adverse Event Details

AEs may be either spontaneously reported or elicited during questioning and examination of a subject. All AEs must be recorded on the AE CRF. If known, the PI should report the diagnosis of the underlying illness or disorder, rather than its individual symptoms. Subjects experiencing AEs that cause interruption or discontinuation of study drug or those experiencing AEs that are present at the end of their participation in the study should receive follow-up as appropriate. AEs should be followed to resolution or stabilization (if possible) and, if they become serious, reported as SAEs. If possible, the outcome of any AEs that caused permanent discontinuation or that were present at the end of the study, especially those considered by the PI to be related to the study drug, should be reported.

Information on the medical condition of subjects should begin following the subject’s written informed consent to participate in the study and a medical history should be taken at screening. During any wash out and baseline periods, any changes in the health of subjects should be recorded as changes in medical history unless an event occurred as a result of a study-related procedure and is unanticipated; in such cases, the event should be recorded as an AE and reported to the Institutional Review Board (IRB) as an “unanticipated problem” in accordance with local procedures. Other changes in subject health information becomes AE data when the subject begins dosing with the study drug; therefore, AE data should be collected from the date of the first dose of study drug until the date of the final study visit. These data are considered treatment-emergent AEs.

The PI will instruct the subject to report any AEs that may occur during the study. At each visit, the PI should ask the subject, in non-directive fashion, about any change in the subject’s overall

health status since the previous visit. Optional photographs may be obtained for areas outside of the face, as clinically indicated for the classification and management of AEs.

The PI will assign a CTCAE grade to all AEs (CTCAE Version 5.0, [Appendix 4](#)). The severity of each AE, as judged by the PI, will be recorded on the appropriate AE CRF and will be graded according to the following scale:

Mild - The AE is usually transient and may require only minimal treatment or therapeutic intervention. The event does not generally interfere with usual activities of daily living.

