7.3. Pregnancy

Male subjects who are not surgically sterile, and are sexually active with a female partner must agree to use an effective method of birth control from the first administration of the study drug until 30 days after the last study drug application. Female subjects who are WOCBP, and are sexually active with a male partner must agree to use an effective method of birth control from the first administration of the study drug until 30 days after the last study drug application. Protocol Section 4.2, Inclusion Criteria #6, provides definitions of sterility and methods of acceptable birth control.

Prior to study enrollment, subjects must be advised of the importance of avoiding pregnancy during study participation and the potential risk factors for an unintentional pregnancy. The subject must sign an informed consent form documenting this discussion.

WOCBP should be instructed to contact the investigator immediately if they suspect they might be pregnant (e.g., missed or late menstrual period) during the study and for 30 days after she has completed her last test article application. If a subject or investigator suspects that a subject may be pregnant at any time during the study, the test article must be withheld until the results of laboratory pregnancy testing are available. If pregnancy is confirmed, the subject must not receive or apply further test article.

If following initiation of study treatment, it is subsequently discovered that a subject was pregnant or may have been pregnant at the time of test article exposure, the investigator must immediately notify the Medical Monitor of this event and record the pregnancy on the appropriate pregnancy surveillance form. The form will be sent to the Sponsor or designee. The investigator must notify the IRB of any pregnancy associated with the study treatment and keep careful source documentation of the event, including abortion (accidental, therapeutic, or spontaneous) and birth of offspring. Offspring should be followed for a minimum of eight weeks and any congenital anomaly/birth defect in a child born to a subject or a male subject's sexual partner that was exposed to the study drug should be documented on the pregnancy surveillance form as appropriate.

During the study, all male subjects should be instructed to contact the PI immediately if they suspect that their sexual partner might be pregnant (e.g., female sexual partner has missed or late menstrual period).

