8.2 Analysis Populations

8.2.1 *Safety Population*

The Safety population will include all randomized subjects who received and applied study drug. Subjects will have their first application of test article applied in the clinic by the PI (or sub-I-designee) during their Baseline Visit on Day 1. Subjects will be included in a treatment group based on the treatment they received (even if not the treatment group to which they were randomized). If a subject administered more than one type of test article during the trial, then the subject will be included in the treatment group to which they were randomized.

8.2.2 *Modified Intent-to-Treat Population*

The modified intent-to-treat (mITT) population will include all randomized subjects who were dispensed the study drug and have at least one post-baseline assessment. Subjects will be included in the treatment group to which they were randomized, regardless of the treatment received.

8.2.3 *Per-Protocol Population*

The per-protocol (PP) population will include a subset of the mITT population who completed the study without significant protocol deviations (as will be determined prior to unblinding the randomization) and met the criteria as specified below. Subjects will be included in the treatment group based on the treatment received.

- Meets all inclusion criteria and does not meet exclusion criteria #1-11 and #13-22.
- Has not taken or applied any interfering concomitant medications/therapies.
- Completed Visit 5/EOT procedures on Days 71 to 90 with the visit occurring 1 to 10 days after the final application of test article.
- Applied at least 80% of the expected doses with no other evidence of material dosing non-compliance.

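### The last safety call is set by study day (Day 106 ±3) but the 30-day SAE and pregnancy windows run from the last application, so the call can precede their close by up to 4 days on the planned schedule

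*Protocol*

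**What the plan says.** Two clocks govern safety follow-up after treatment.

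**Study-day clock.** Protocol 6.2.4 describes the follow-up contact as "Visit 6 (Week 16/End of Study/Day 106"), made by telephone. Appendix 2 and SAP Table 1 allow ±3 days, that is Days 103 to 109. Nothing ties the call to the last application or to the actual date of Visit 5. Protocol 7.2 makes this the end of routine collection: "AE data should be collected from the date of the first dose of study drug until the date of the final study visit". For a subject who completes the schedule, that final visit is the call.

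**Last-dose clock.** Protocol 7.2.2 covers an SAE "that occurs within 30 days after stopping the study drug", introduced by the condition "Should the PI become aware of an SAE". Protocol 7.3 requires contraception "until 30 days after the last study drug application" and tells women of childbearing potential to contact the investigator about a suspected pregnancy "during the study and for 30 days after she has completed her last test article application". SAP 8.12.2 also uses this clock: in certain cases it caps an imputed AE start date at 30 days after the last dose.

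The link between the clocks is the day of the last dose. Protocol 5.3 and Appendix 2 (footnotes p and q) put Visit 5 at 3 to 7 days after the final application. SAP 8.8 turns this into a planned final dose on Study Days 73 to 77.

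**The concern.** Safety and tolerability form the primary objective. The product is a live organism, and Protocol 1.4 lists opportunistic infection, described as unlikely, among the risks. The protocol treats 30 days after the last application as the relevant period for SAEs and pregnancy, but no scheduled contact is placed to cover it. A subject who follows the plan exactly, dosing through Day 77 and attending Visit 5 on Day 80, has a window that closes on Day 107, one day after the target date of the call.

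Once the call has been made, an event in the remaining days is recorded only if the subject volunteers it or the investigator happens to hear of it. Subjects who finish dosing later are actively questioned over a shorter period after their last dose. With 36 subjects, it is worth having that period cover the protocol's own limit for everyone.

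**Working it through.** **Inputs**
- Call day C: 103 to 109, target 106 (Protocol 6.2.4, Appendix 2).
- Window length: 30 days from the last application (Protocol 7.2.2 and 7.3).
- Gap from last dose to Visit 5: 3 to 7 days (Protocol 5.3, Appendix 2 footnotes p and q).
- Visit 5 target: Day 80 (Appendix 2, SAP Table 3).

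**Step 1: reproduce the SAP's last-dose range.** Last dose L = Visit 5 day minus the gap: 80 − 7 = 73 and 80 − 3 = 77. This matches Days 73 to 77 in SAP 8.8.

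**Step 2: shortfall on the planned range.** The window closes on day L + 30. Shortfall = (L + 30) − C, counted when positive.

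| Last dose L | Window closes | Call days before close | Shortfall at Day 103 | Shortfall at Day 106 |
|---|---|---|---|---|
| 73 | 103 | 0 of 7 | 0 | none |
| 74 | 104 | 1 of 7 | 1 | none |
| 75 | 105 | 2 of 7 | 2 | none |
| 76 | 106 | 3 of 7 | 3 | 0 |
| 77 | 107 | 4 of 7 | 4 | 1 |

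The call is early in 0 + 1 + 2 + 3 + 4 = 10 of 5 × 7 = 35 combinations. The maximum is 4 days, and a call on Day 109 is never early. Questioning covers between 103 − 77 = 26 and 109 − 73 = 36 days after the last dose. The 35 combinations are a count of what the schedule permits. They are not equally likely and do not give a probability.

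**Step 3: wider reading of the Visit 5 window.** Appendix 2 prints +3 to +7 days in the Visit 5 column, above Day 80. Read as an offset from Day 80, it puts Visit 5 on Days 83 to 87. Then L runs from 83 − 7 = 76 to 87 − 3 = 84, and the windows close on Days 106 to 114. The largest shortfall is 114 − 103 = 11 days at the earliest call, 114 − 106 = 8 at the target and 114 − 109 = 5 at the latest. The early call days for L = 76, 77, 78 and 79 are 3, 4, 5 and 6, and for each of L = 80 to 84 they are 7. The total is 18 + 35 = 53 of 9 × 7 = 63 combinations.

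**Step 4: sensitivity case outside the schedule.** The SAP per-protocol rule accepts subjects who "Completed Visit 5/EOT procedures on Days 71 to 90". With Visit 5 on Day 90 and the protocol's 3-day minimum gap, L = 87, the window closes on Day 117, and the shortfall is 117 − 103 = 14 days at most and 117 − 109 = 8 at least. With the 1-day gap that the SAP rule tolerates, L = 89 and the maximum is 119 − 103 = 16 days.

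**The case against.** **The call can be up to two weeks early.** A reader might infer this by combining the SAP's Day 90 limit with the Day 103 call, as in Step 4. The documents do not support it as a feature of the design. The Day 90 limit decides which subjects enter the per-protocol analysis and authorises neither a late visit nor extra dosing. A 14-day shortfall needs a last dose on Day 87 or later, which lies outside the SAP's Days 73 to 77 and outside even the wider reading of Appendix 2.

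**SAE or pregnancy reporting stops at the call.** This is also tempting and also wrong. The SAE clause applies to anything the investigator learns of within the 30 days, whether before or after Visit 6, and the pregnancy instruction to subjects still runs "for 30 days after she has completed her last test article application". Neither clause requires a scheduled contact at day 30, so the passages do not strictly contradict each other.

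**The planned gap is small.** This stands. A last dose on Day 77 is the least favourable planned case. At the target call day it is the only case that falls short, and by one day. A fixed call with at least 26 days of follow-up is a coherent choice, broadly in line with the four-week follow-up period in Protocol 3.5. The documents give no latency that would make the last few days critical, and nothing suggests that the interval would differ between blinded arms.

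**The 11-day figure rests on the weaker reading.** This is largely right. Footnote p measures the 3 to 7 days from the final application, SAP 8.8 does the same, and a last dose after Day 77 would exceed 11 weeks of dosing. The column header nevertheless remains open to the other reading.

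**Conclusion.** The point holds as a small mismatch between two clocks. On the planned last-dose range the call can precede the close of the 30-day windows by up to 4 days, and by 1 day at the target for a subject who doses through Day 77. The figure of 11 days applies only if the Appendix 2 header moves Visit 5 to Days 83 to 87 and dosing continues past Day 77. Longer gaps arise only from departures from the schedule.

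What ends early is active solicitation of events, not the duty to report them. No bias between arms is shown.

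The figures assume that a call on the closing day itself counts as covering the window, and they apply to subjects who complete the schedule. Protocol 3.6 describes the Week 16 call for those subjects and does not state there whether early discontinuers receive one. This is a minor, inexpensive improvement to follow-up for the primary objective.

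**What to change.** Reconcile the two clocks. Time the Visit 6 telephone call from the recorded date of last application, so that it does not precede the end of the 30-day window the protocol already sets. For last doses on Days 73 to 77 this means a call no earlier than Days 103 to 107 respectively. Carry the change into Protocol 6.2.4, Appendix 2 and SAP Table 1. State in Appendix 2 and SAP Table 1 whether +3 to +7 days is measured from the final application or from Day 80. Because AE collection ends at the final visit, it would then follow the same clock without a separate change.

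The cost is a wording amendment and a call a few days later for some subjects, with no added visit. On the planned range the Day 106 target moves by at most one day. Protocol 3.3 already speaks of randomisation in the past tense, so the calls may have been made. In that case, tabulate days from last application to last safety contact by arm in the study report, so that readers can see how far solicited follow-up covered the 30 days.
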